#### 4.3. Sample Size Considerations

A total of approximately 40 subjects is planned in this crossover study. The sample size for the study parts are based on practical considerations. No formal hypothesis testing is planned.

The crossover design allows for an increased level of precision in estimates as compared to a parallel design with the same number of subjects. For primary and cognition related secondary endpoints, a sample size of 20 subjects in each cohort provides at least 80% power in this cross-over design to detect a treatment difference of  $0.79*SD$  (active versus placebo) or larger for each endpoint of interest, where SD represents the standard deviation for the endpoint of interest.

For cognition related secondary endpoints, a sample size of 40 subjects overall (both cohorts combined) provides at least 80% power in this cross-over design to detect a treatment difference of  $0.54*SD$  (active versus placebo) or larger for each endpoint of interest. Sample size assumptions were based on a 2-sided t-test with a Type I error rate of 5%, equal (or no) carryover effects, and a correlation of at least 0.3 between study periods. No adjustments were made for dropouts or multiplicity.

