- ATT Difficulty Multiplier Mean (Phase 2B): The mean of the difficulty multiplier calculated over the entire 2B assessed phase of the task. This measure is only calculated during the times that either ‘Finger/Lift’ and/or ‘Multi-touch’ are not occurring. The measurement name for this parameter in the files downloaded from the CANTAB portal is ATT2BDM.
- ATT Difficulty Multiplier Standard Deviation (Phase 2B): The standard deviation of the difficulty multiplier calculated over the entire 2B assessed phase of the task. This measure is only calculated during the times that either ‘Finger Lift’ and/or ‘Multi-touch’ are not occurring. The measurement name for this parameter in the files downloaded from the CANTAB portal is ATT2BDSD.
- SST Stop Signal Reaction Time: The estimate of time where an individual can successfully inhibit their responses 50% of the time. This covert measurement is sampled from the length of time between the go stimulus and the stop stimulus at which the subject is able to successfully inhibit their response on 50% of the trials. We can infer that this is the time before which all actions become ballistic and the subject is no longer able to cancel their action selection. The measurement name for this parameter in the files downloaded from the CANTAB portal is SSTSRT.
- SST Median RT: All Go Trials: The median reaction time taken across all the valid Go trials in the task. The measurement name for this parameter in the files downloaded from the CANTAB Portal is SSTMRTG.

In addition to the descriptive statistic summaries for the above, for each parameter, a mixed effects model approach will be used to evaluate treatment effect. The model will include change from baseline as the dependent variable, baseline as a covariate, treatment sequence, period, timepoint (i.e, Day 1: 4 hrs post-dose, Day 7: 4 hrs post-dose, Day 14: 4 hrs post-dose), disease type, and treatment as fixed effects, and subject as a random effect. The least square means will be summarized, as well as the least square mean difference between treatments, where the

Sponsor: CuraSen Therapeutics, Inc.  
Protocol Number: CST103/CST107-CLIN-011  
Version and Date: [REDACTED] v1.0 / 24May2022

corresponding p-value for this LS mean difference will be provided. All inferential analyses are exploratory in nature given that this study was not powered based on any statistical assumptions.

Line plots detailing individual subject results of the ATT parameters will be produced.

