### *Verbal Fluency Test*

The 'ALPHABET' and 'CATEGORY' tests from the Brief and Simple Index of Cognition (BASIC) tests are used in this study. For the ALPHABET task, subjects are given one minute to say aloud as many words they can think of that begin with the letter F, avoiding repetitions or the same words with different endings. The total score is the number of correct words generated. For the CATEGORY task, subjects are given 1 minute to say aloud as many animals they can think of, avoiding repetitions. The total score is the number of animals generated.

Similar to the CANTAB data, descriptive summaries for the ALPHABET and CATEGORY total scores (identified in the raw data as AAACCPT and CAACCPT, respectively) and change from baseline will be provided at each collection timepoint (i.e, Day 1: 4 hrs post-dose, Day 7: 4 hrs post-dose, Day 14: 4 hrs post-dose), and a mixed effects model with change from baseline as the dependent variable, baseline as a covariate, treatment sequence, period, timepoint, disease type, and treatment as fixed effects, and subject as a random effect. The LS mean, LS mean difference, and p-value for the difference will be reported.

Verbal fluency data will be listed on the FAS.

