#### *Geriatric Depression Scale (GDS)*

The GDS is a 30-item self-administered yes/no question test constructed for brief screening of depression in elderly persons. Total scores are the summation of scored responses (responses indicating worsening depression equate to 1, and responses indicating lessening depression equate to 0) from each question. Scores greater than 9 are considered suspect for depression. The GDS will be administered on Day 1 (Baseline), Day 7, and Day 14 of each treatment period. Summary statistics of total scores and change from baseline will be presented. A mixed model with change from baseline as the outcome, baseline as a covariate, fixed effects for treatment sequence, period, timepoint (i.e., Day 7, Day 14), disease type, and treatment, and subject as a random effect will be analyzed. LS mean, LS mean difference and its associated p-value will be reported.

All GDS data, included responses to individual questions, will be listed.

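### The single baseline slope in the SAP 8.2 crossover models can cost precision, by an amount the documents do not fix, and the repeated-timepoint models also need a subject-by-period term

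*SAP*

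**What the plan says.** **Model.** SAP 8.2 (CANTAB) states: "The model will include change from baseline as the dependent variable, baseline as a covariate, treatment sequence, period, timepoint". Disease type and treatment complete the fixed effects, and subject is the only random effect. Verbal fluency has "a mixed effects model with change from baseline as the dependent variable, baseline as a covariate" and GDS has "A mixed model with change from baseline as the outcome, baseline as a covariate", with the same remaining terms. ESS matches. The pupil and HADS paragraphs list the same terms without naming the dependent variable.

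**Baseline.** SAP 6.3 takes the last value up to the start of treatment. SAP 6.1 gives each period its own treatment start date. SAP 8.2 labels the Day 1 pre-dose assessment of each period as baseline. Protocol 8.5 allowed either a within-period or a pre-study baseline and left the choice to the SAP. SAP 6.3 never says within period outright.

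**Post-dose values per period.** Three for CANTAB, fluency and pupil; two for ESS and GDS; one for HADS.

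**Precision.** SAP 4.3 justifies the crossover by its precision. It says that "a sample size of 20 subjects in each cohort provides at least 80% power in this cross-over design" for a difference of 0.79 SD, and that "a sample size of 40 subjects overall (both cohorts combined) provides at least 80% power" for 0.54 SD, with a between-period correlation of at least 0.3.

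**The concern.** In a two-period crossover with sequence and period fitted, the treatment effect is a within-subject contrast. The useful baseline slope is therefore the within-subject one: how far the difference between a subject's two baselines predicts the difference between that subject's two outcomes. Across subjects, baseline usually predicts outcome much more strongly. One common slope is pulled toward that steeper relation, so the model over-corrects the contrast and carries baseline noise into the treatment estimate.

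Modelling change instead of the raw value does not help. With baseline as a covariate, the slope shifts by one and the treatment estimate is identical. For the same reason, the unnamed dependent variable in the pupil and HADS models does not matter here.

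At stake is part of the precision for which the crossover was chosen, in the models that give p-values for 16 CANTAB measures and for fluency, ESS, pupil, GDS and HADS.

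**Working it through.** **1. The plan's own figures.** The SD of a within-subject difference at correlation 0.3 is SD × √(2 × 0.7) = 1.183 SD. With a noncentral t on n − 2 df, power is 0.806 for 0.79 SD at n = 20 and 0.803 for 0.54 SD at n = 40. Both figures reproduce.

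**2. Variance model (assumed).** Within a period, baseline is B = s + w + e₀ and each of T post-dose values is Y = s + w + e. Total variance is 1.
- var(s) = ρ, the between-period correlation.
- var(w) = f(1 − ρ), where f is the share of the remaining variance common to baseline and response within a period.
- var(e) = (1 − f)(1 − ρ).

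Only the floor of 0.3 for ρ comes from the documents. Higher ρ and every f are assumptions.

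**3. Formulas (large sample).**
- The correct within-subject slope is f.
- At slope b, the within-subject variance of a period mean is P(b) = var(w)(1 − b)² + b² var(e) + var(e)/T. The treatment variance is proportional to P(b).
- The variance of a subject mean is M(b) = ρ(1 − b)² + P(b)/2.
- The model's residual variance is V(b) = [T P(b) + 2(T − 1) var(e)]/(2T − 1).
- The one-slope model picks the b that minimises (2T − 1) ln V(b) + ln[2T M(b)].
- Loss ratio = P(fitted b)/P(f).

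Example with ρ = 0.7, f = 0, T = 3: var(e) = 0.3 and the fitted b is 0.40 against a correct slope of 0. P(0.40) = 0.16 × 0.3 + 0.1 = 0.148 and P(0) = 0.100, a ratio of 1.48 (1.49 unrounded).

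**4. Variance of the planned model divided by that of the split-baseline model, for f = 0 / 0.25 / 0.5 / 0.75.**

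| ρ | T = 1 (HADS) | T = 2 (ESS, GDS) | T = 3 (CANTAB, fluency, pupil) |
|---|---|---|---|
| 0.3 | 1.07 / 1.05 / 1.03 / 1.01 | 1.09 / 1.05 / 1.03 / 1.01 | 1.10 / 1.05 / 1.02 / 1.01 |
| 0.5 | 1.20 / 1.13 / 1.08 / 1.03 | 1.25 / 1.14 / 1.08 / 1.03 | 1.23 / 1.12 / 1.07 / 1.03 |
| 0.7 | 1.44 / 1.27 / 1.16 / 1.07 | 1.58 / 1.33 / 1.18 / 1.08 | 1.49 / 1.29 / 1.16 / 1.07 |
| 0.8 | 1.61 / 1.37 / 1.21 / 1.09 | 1.94 / 1.50 / 1.26 / 1.11 | 1.84 / 1.49 / 1.26 / 1.11 |

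In terms of sample size with T = 3, 20 subjects are worth 20/1.10 = 18 at ρ = 0.3 and f = 0. At ρ = 0.8 they are worth 20/1.84 = 11 with f = 0, or 20/1.26 = 16 with f = 0.5.

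At the plan's own ρ = 0.3 with f = 0 and T = 1, the fitted b is 0.26, so P rises from 0.70 to 0.70 × (1 + 0.26²) = 0.747. Power for 0.79 SD at n = 20 falls from 0.806 to 0.780.

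**5. Simulation check (REML).** With n = 20, T = 3 and f = 0 (1,200 runs per cell), the ratio is 1.08, 1.25, 1.49 and 1.74 at ρ = 0.3, 0.5, 0.7 and 0.8. For one post-dose time at n = 20 and f = 0 (600 runs per cell), it is 1.19, 1.29 and 1.32 at 0.5, 0.7 and 0.8. Bias was negligible. The few ratios below 1 occurred at ρ = 0.3 and are within simulation error.

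**6. Standard error when T exceeds 1.** The model's variance for the treatment effect, relative to the true one, is V(b)/[T P(b)]. Take ρ = 0.7, f = 0.25, T = 3, so var(w) = 0.075 and var(e) = 0.225.
- Planned model: 0.55. The nominal 5% test has size P(|Z| > 1.96 × √0.55) = 0.15.
- After the split: P(0.25) = 0.0422 + 0.0141 + 0.075 = 0.1313 and V = (3 × 0.1313 + 4 × 0.225)/5 = 0.259. The ratio is 0.259/0.394 = 0.66 and the size is P(|Z| > 1.96 × √0.66) = 0.11.
- With f = 0 the split brings this ratio to 1 and the size to 5%.

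Simulated size after the split is about 0.08-0.18 with two or three timepoints and shared within-period variation.

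**The case against.** The strongest reply is that the only documented correlation is 0.3, where the ratio is about 1.0-1.1 and the power loss is under three points. That stands, and the range must start there. But 0.3 is stated as a minimum, so higher values fall within the plan's own assumption.

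Second, the large ratios need little shared within-period variation. The Day 1 baseline and the first post-dose CANTAB, fluency and pupil tests are hours apart, so f above 0 is plausible. That also stands. At ρ = 0.7 and T = 3 the ratio falls from 1.49 at f = 0 to 1.07 at f = 0.75, and one simulation at n = 20 with f = 0.75 gave 1.01. With f = 0.5 the one-slope model also beats using no baseline.

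Third, a pre-study baseline would be constant within a subject, and the problem would not arise. SAP 6.1 and 8.2 make the period-specific reading the better one, but SAP 6.3 should say so.

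Fourth, the SAP calls all this inference exploratory, protocol 8.7 permits baseline values as appropriate, and one baseline covariate is a common choice. This limits the consequence and means that the model is no departure from the protocol. It is not a reason to keep a noisier estimator when the change is so small.

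A reader might infer that the treatment estimates are biased, or that the crossover's advantage is largely lost. Neither is supported. Under equal carryover the estimate is unbiased, and a large loss needs both high correlation and little shared within-period variation, which the documents do not establish. Nor does the point reach BioStamp, which has one baseline period per subject.

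**Conclusion.** The point holds as a possible loss of precision in six sets of exploratory secondary analyses: CANTAB, verbal fluency, ESS, pupil, GDS and HADS. Relative to a split-baseline model, the planned variance is about 1.0-1.1 times at correlation 0.3, 1.03-1.3 at 0.5, 1.07-1.6 at 0.7 and 1.1-1.9 at 0.8. Each range runs from much shared within-period variation (low end) to none (high end). At high correlation the loss is smaller for the single HADS value; two timepoints behave much like three. All of this rests on the period-specific reading of baseline, on the simple variance model above, and on correlations that the documents do not give beyond the floor.

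A reader might also infer that splitting the baseline repairs the p-values. It does so only when values within a period are no more alike than the subject effect explains. Otherwise, in the models with two or three timepoints, the standard error stays too small and the subject-by-period term is needed as well.

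**What to change.** 1. In SAP 6.3, state that baseline for CANTAB, verbal fluency, ESS, pupil, GDS and HADS is the Day 1 pre-dose value of each period.
2. In each of these models, replace the baseline term by two covariates: the subject's mean of the period baselines, and the period baseline minus that mean (0 for a subject with one period).
3. In the models with more than one post-dose timepoint per period (all but HADS), add a subject-by-period random effect.

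Leave the BioStamp model as it is.

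The cost is a few SAP sentences, one degree of freedom per model, and one variance component in the repeated-timepoint models. Their standard errors become somewhat larger but valid. No new data are needed.

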Preliminary data show that once-weekly dosing of 80 µg CST-103 for 2 weeks resulted in increases of cerebral perfusion in three subjects with PD on Days 1 and 7. Furthermore, persistent increases in cerebral perfusion were noted in healthy volunteers at 24 and 48 hours after administration of 80 µg CST-103 (CLIN-002, Cohort 5). Since a single dose of 80 µg of CST-103 produces a robust increase in cerebral perfusion which lasts a few days after dosing (Figure 1), the expectation is that the positive cognitive effects seen after administration of a single dose of either 80 or 160 µg CST-103 may also be demonstrated with the 80 µg dose of CST-103 administered daily. In summary, a dose of 80 µg of CST-103 administered daily has been shown to be safe and well tolerated from previous data from the literature and in the CuraSen clinical studies CLIN-002 and CLIN-003.

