2. STUDY OBJECTIVES AND ENDPOINTS

2.1. Study Objectives

The primary objective of this study is to identify a CNS signal in one of the planned pharmacodynamic measurements after multiple oral doses of CST-103 in the presence of CST-107 in four populations of subjects with Neurodegenerative Disorders (NDD):

Cohort A

1. Parkinson's Disease (PD) with REM Sleep Behavior Disorder (RBD) and Depressive Symptoms
2. Mild Cognitive Impairment (MCI) with Depressive Symptoms

Cohort B

3. Dementia with Lewy Bodies (DLB) with Cognitive Fluctuations
4. Parkinson's Disease Dementia (PDD) with Cognitive Fluctuations

These pharmacodynamic assessments will compare the effect of CST-103 co-administered with CST-107 with that of placebo on the following:

Cohort A

- Emotional Facial Processing

Cohort B

- Cognitive fluctuations

The secondary objectives for all subjects include the comparison of the effect of CST-103 co-administered with CST-107 with that of placebo on the following:

1. Cognition
2. Movement and time spent sitting, standing and sleeping
3. Sleep
4. Pupillary reactivity
5. Mood Assessment
6. Safety and tolerability of CST-103 co-administered with CST-107
7. The pharmacokinetic (PK) profiles of CST-103 and CST-107

The exploratory objectives are to characterize the effect of CST-103 co-administered with CST-107 on the following:

1. To characterize the effect of CST-103 co-administered with CST-107 on inflammatory biomarkers in blood, such as C-reactive protein and cytokine levels may be measured.
2. To characterize the effect of CST-103 co-administered with CST-107 on neurodegenerative biomarkers in the blood such as neurofilament light chain, total and phosphorylated tau protein, and amyloid- β ($A\beta$) peptides may also be evaluated.
3. To characterize the effect of CST-103 co-administered with CST-107 on performance of a sustained attention task in Cohort B subjects.
4. To characterize the effect of CST-103 co-administered with CST-107 on Freezing of Gait (FOG) (for subjects with RBD+PD, PDD and DLB).
5. To characterize the locus coeruleus volume and contrast ratio (this is an optional objective based on imaging capabilities).

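### The CANTAB, verbal fluency and pupil models average the first-dose response with Days 7 and 14, and no model-based contrast is planned for repeated dosing

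*SAP*

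**What the plan says.** In SAP 8.2 the CANTAB model takes change from baseline as the outcome and adjusts for the baseline value, with period and sequence as factors and subjects random. The visit and treatment terms read: "timepoint (i.e, Day 1: 4 hrs post-dose, Day 7: 4 hrs post-dose, Day 14: 4 hrs post-dose), disease type, and treatment as fixed effects". Its output is the LS means, their difference between treatments and a p-value. Verbal fluency and pupillary diameter use the same terms and the same three post-dose timepoints. None of the three has a treatment-by-timepoint interaction or a visit-specific contrast.

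ESS and GDS differ. Day 1 is their baseline, and the GDS model has "fixed effects for treatment sequence, period, timepoint (i.e., Day 7, Day 14), disease type, and treatment"; ESS uses the same two visits. HADS is modelled at Day 14, its only post-baseline visit within a period.

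Protocol 2.1 gives the primary objective as to "identify a CNS signal in one of the planned pharmacodynamic measurements after multiple oral doses of CST-103". Protocol 1.4.2.1 adds, for cognition, that "the expectation is that the positive cognitive effects seen after administration of a single dose" may also appear with daily 80 µg dosing.

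**The concern.** The protocol distinguishes a single dose from repeated daily dosing and wants to know whether effects are present under the latter. For cognition and pupil, the one planned treatment difference mixes the two. An effect that builds over two weeks is diluted by a null Day 1. An effect present after the first dose and then lost still gives a non-zero pooled difference, which can be taken as evidence for daily dosing. The reported number cannot tell these cases apart, or separate either from a steady effect.

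These secondary models carry much of the inference in this SAP. FERT and EEG are sent to separate analysis plans, and the Cohort B primary data are listed only.

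**Working it through.** **1. The SAP's own power.** Inputs from SAP 4.3: "2-sided t-test with a Type I error rate of 5%, equal (or no) carryover effects, and a correlation of at least 0.3 between study periods"; 0.79 SD with 20 subjects; 0.54 SD with 40.
- SD of the within-subject active-placebo difference = SD × √(2(1 − 0.3)) = 1.183 SD.
- Noncentrality = √n × d / 1.183.
- n = 20: 4.472 × 0.79 / 1.183 = 2.986, 18 df, power 80.6%.
- n = 40: 6.325 × 0.54 / 1.183 = 2.886, 38 df, power 80.3%.

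The stated 80% reproduces, for a paired contrast with one value per period.

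**2. What the additive model estimates.** With complete, balanced data the treatment term is (Δ1 + Δ7 + Δ14)/3 for CANTAB, verbal fluency and pupil, and (Δ7 + Δ14)/2 for ESS and GDS. This was checked by fitting the models to almost noise-free crossover data with true effects of 0, 0.395 and 0.79 SD at Days 1, 7 and 14:
- additive model, three visits: 0.395 SD, half the Day 14 effect;
- with treatment-by-timepoint: 0.00, 0.395 and 0.79 SD;
- additive model, Days 7 and 14 only: 0.593 SD, since (0.395 + 0.79)/2 = 0.5925.

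**3. Size of the averaging, with illustrative power.** Assumptions that are not in the documents: the visit profile, and a correlation r between visits of the within-subject differences. The pooled-to-single-visit SE ratio is √((1 + 2r)/3), which is 0.816, 0.894 and 0.966 for r = 0.5, 0.7 and 0.9. The noncentrality is 2.886 × (pooled effect/D) / SE ratio, with n = 40, D = 0.54 SD and 38 df. For 0, D, D and r = 0.5 it is 2.886 × 0.667 / 0.816 = 2.36, giving 63%.

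| Effect at Days 1, 7, 14 | Pooled estimate | Pooled power, r = 0.5 / 0.7 / 0.9 | Day 14 contrast alone |
|---|---|---|---|
| D, D, D | D | 93 / 88 / 83% | 80% |
| 0, D, D | 0.67 D | 63 / 55 / 49% | 80% |
| 0, 0, D | 0.33 D | 21 / 18 / 16% | 80% |
| D, 0, 0 | 0.33 D | 21 / 18 / 16% | 5% (true effect 0) |
| D, D/2, 0 | 0.50 D | 41 / 35 / 31% | 5% (true effect 0) |

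With n = 20 and 0.79 SD the results agree within 1 percentage point.

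**4. Standard error.** Step 3 presumes a valid test of visit-averaged period differences. The SAP names a random subject effect only, so three visits in one period are treated as independent given subject. Simulating that model under the step 3 variances, without the baseline covariate, gave null rejection rates of roughly 22% to 37% as r rose from 0.5 to 0.9, against a nominal 5%. A period-specific baseline covariate could absorb part of this excess; how much is unknown.

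**The case against.** The phrase about multiple doses belongs to the primary objective, whose measures are facial emotion processing and cognitive fluctuations. The criticised models serve secondary objectives, which name no day or dose count. This stands as a limit on severity. It does not remove the point, because the dose rationale in Protocol 1.4.2.1 poses single versus daily dosing for cognition specifically.

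That rationale expects an effect seen after one dose to persist, which is closest to the constant profile, where pooling gains precision. This also stands, and is why the average should be kept. The harmful case most in keeping with the rationale is an effect that fades after Day 1, and the pooled estimate hides it.

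The SAP plans descriptive values and changes at each assessment, and Protocol 8.7 and 8.8 permit paired t-tests or nonparametric comparisons. A reader might infer that the repeated-dose effect is never estimated; that is too strong. What is missing is a committed model-based difference by visit. The CANTAB section also presents its summaries by treatment sequence, whereas the opening of SAP 8 says by treatment at the time of collection, so the descriptive tables may not show active against placebo directly.

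A reader might extend the point to ESS and GDS. The documents do not support that: both models use Days 7 and 14 only and already estimate an effect of repeated dosing. Nor does the Day 14-only HADS model reveal an inconsistency, because HADS has no Day 7 assessment.

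**Conclusion.** The point holds for CANTAB, verbal fluency and pupil: 24 measures whose only planned model-based difference gives one third of its weight to the single-dose response. That weight follows from the model, given complete data. The dilution factors (0.67 and 0.33) follow once a visit profile is assumed. The power figures are illustrative only, since they rest on assumed profiles, assumed correlations and a valid standard error, which the stated random-effects structure may not give. The sample-size statement is unaffected.

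All inference here is declared exploratory and unadjusted, so this is a change that should be made rather than a flaw that invalidates the plan. The label does not alter what the model estimates.

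**What to change.** In SAP 8.2, for the CANTAB, verbal fluency and pupil models:
- add a treatment-by-timepoint term and report the active-placebo LS mean difference with 95% CI at each visit;
- name one repeated-dose contrast in advance, either Day 14 or the Day 7/14 average;
- label Day 1 at 4 hours as the acute single-dose contrast;
- keep the all-visit average as supportive;
- allow for correlation among visits within a period, for example with a subject-by-period random effect.

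By-visit contrasts for ESS and GDS are optional. HADS needs no change.

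The cost is SAP wording and programming, with no new data. Single-visit intervals are wider than the pooled one if the effect is constant. The tables would grow from 24 treatment differences to 72 (24 × 3) plus the 24 retained averages, all unadjusted, which is the reason to name the main contrast before unblinding.
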